16.1.4. SENSITIVITY ANALYSIS OF PRIMARY EFFICACY VARIABLE

The primary endpoint will be presented for the following:

- Subgroup analysis will be performed by subgroups, including data imputation described in Sections 7.5 and 16.1.2 of the SAP, respectively.
- Observed data analysis will be performed by the following subgroups:
 - Analysis with no data imputation, including all patients with data collected, on treatment or not, and at required timepoint or at EOS visit (excluding patients with missing data).
 - Analysis with no data imputation, including only patients with data collected at the required visit while still on randomized treatment at scheduled visit, or at end of study visit within the visit window.
- Average imputation, as described in Section 16.1.2 of the SAP.
- Analysis with tipping point approach, as described in Section 16.1.2 of the SAP.
- Analysis with multiple imputation, as described in Sections 16.1.2 and 16.1.3 of the SAP, based on PP population.

[REDACTED]

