9.2 Sample Size Determination

Approximately 800 patients will be randomized. The standard deviation for the change in FEV₁ AUC_{0-12h} is estimated to be 250 mL. With a 2-sided test at a 5% significance level and 500 vs. 300 evaluable patients in the two groups, there will be an 90% power to detect a true difference of 59 mL between the treatments. If the withdrawal rate at 24 weeks exceeds 25% overall, additional patients may be randomized to the study to compensate for the loss of data.

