7.5. EXAMINATION OF SUBGROUPS

Subgroup analyses will be conducted as stated in the efficacy analysis and disposition sections.

[REDACTED]	[REDACTED]	[REDACTED]	[REDACTED]
[REDACTED]	[REDACTED]	[REDACTED]	[REDACTED]
[REDACTED]	[REDACTED]	[REDACTED]	[REDACTED]
[REDACTED]	[REDACTED]	[REDACTED]	[REDACTED]

Primary aim for the subgroup analysis is to check whether there are differences in treatment effect between strata or subgroups, which will be tested through interaction. For each analysis by subgroup the results will be summarized as follows:

- Complete data with added fixed effect to the model: subgroup*treatment.
- Data split by subgroup using the main model.

The following subgroups will be assessed and described within the analysis Sections 16.1.4 and 16.2.4 of the SAP.

- Gender at birth:
 - Female
 - Male
- Age-class (years):
 - <65
 - ≥65
- Region
 - Asia
 - Europe
 - North America
- Actual Background medication strata
 - Yes
 - No
- Actual Smoking strata
 - Current
 - Former
- Actual ICS use
 - Yes
 - No
- Known chronic bronchitis
 - Yes
 - No
- FEV₁ reversibility at screening (≥12% and ≥200mL increase in FEV₁)
 - Yes
 - No
- COPD severity

[Redacted content]

- Mild (post-bronchodilator dose $FEV_1 \geq 80\%$ predicted)
- Moderate ($50\% \leq$ baseline $FEV_1 < 80\%$ predicted)
- Severe ($30\% \leq$ baseline $FEV_1 < 50\%$ predicted)
- Very severe (baseline $FEV_1 < 30\%$ predicted)

All the four categories of COPD severity will be included in the patient disposition presentations. However, when used in efficacy analysis, only the two subgroups with moderate and severe patients will be used in the analysis models.

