16.1.2. MISSING DATA METHODS FOR PRIMARY EFFICACY VARIABLE

The main analysis for the primary endpoint will include estimates from missing data imputation described below. This is done to investigate the influence of missing data due to drop-outs. Only patients with non-missing baseline will be included in the analysis.

The primary analysis will be analyzed using MI based on the missing data assumption Missing at Random (MAR). This process will follow four steps:

1. Partially impute the data for a monotone missing pattern with 100 as a number of imputations and “20905” as seed number. Employ the Markov Chain Monte Carlo (MCMC) method with treatment, region, background medication strata, smoking strata, baseline FEV_1 and average FEV_1 AUC_{0-12h} at Week 12.

1.1 The following SAS codes will be used:

```
proc mi data=<data1> out=<data2> nimpute=100 seed=20905;
  var <treatment> <region> <BackgroundMedStrata> <SmokingStrata>
  <baseline> <visits>;
  mcmc impute=monotone chain=multiple;
run;
```

2. Impute the monotone data using a regression imputation model. Apply by imputation using seed number “20905” with treatment, region, background medication strata, smoking strata, baseline FEV_1 and average FEV_1 AUC_{0-12h} at Week 12.

The following SAS codes will be used:

```
proc mi data=<data2> out=<dataout> nimpute=1 seed=20905;
  by imputation ;
  class <treatment> <region> <BackgroundMedStrata>
  <SmokingStrata>;
  var <treatment> <region> <BackgroundMedStrata> <SmokingStrata>
  <baseline> <visits>;
  monotone regression;
run;
```

3. Each multiple imputed dataset in Step 2 will be analyzed separately, as described in Section 16.1.3 of the SAP.
4. The estimates (LS means, SE, CI, and p-value) from the model analysis in Step 3 will be combined using Rubin’s combination rules for statistical inference.

Sensitivity analysis will be done using:

- Average imputation will be based on data collected on treatment at required visit, or at early termination visit. This will be done on patient level. If there is no such data available, impute with average change from baseline for the particular visit in the opposite randomized treatment group.

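### The primary-endpoint subgroup interaction test runs on values imputed without that interaction, which with similar missingness in the two arms shrinks the estimate by about the imputed share and costs power

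*SAP*

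**What the plan says.** SAP 7.5 gives the purpose: "Primary aim for the subgroup analysis is to check whether there are differences in treatment effect between strata or subgroups". The test is made through interaction, and the pooled version is specified as "Complete data with added fixed effect to the model: subgroup*treatment". A second version splits the data by subgroup and fits the main model in each part. Nine factors are listed: gender, age class, region, background medication, smoking, ICS use, chronic bronchitis, reversibility and COPD severity.

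SAP 16.1.4 then says for the primary endpoint: "Subgroup analysis will be performed by subgroups, including data imputation described in Sections 7.5 and 16.1.2 of the SAP, respectively". The imputation in SAP 16.1.2 is done "with treatment, region, background medication strata, smoking strata, baseline FEV_1 and average FEV_1 AUC_{0-12h} at Week 12". The SAS code there lists the same variables, with no interaction term and no processing by subgroup.

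Region, background medication and smoking are thus main effects in the imputation model, and the other six factors are not in it. For key secondary endpoints, SAP 16.2.2.1 adds every scheduled visit of the parameter to the imputation model.

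**The concern.** The analysis model contains a term that the imputation model lacks. A patient whose Week 12 value is imputed receives the overall treatment effect whatever the subgroup, so the imputed share of the data is generated under no difference between subgroups. That is the hypothesis the analysis is meant to test. At stake are the size of the interaction estimates, the power of the interaction tests, and, for the six omitted factors, the direction of the error. The subgroup results describe how consistent the effect is, and an artefact of imputation would make it look more uniform than the observed data show.

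**Working it through.** **Inputs.** Protocol 9.2: "With a 2-sided test at a 5% significance level and 500 vs. 300 evaluable patients in the two groups"; the SD of the change in FEV1 AUC0-12h "is estimated to be 250 mL"; "90% power to detect a true difference of 59 mL between the treatments". SAP 16.1.2: the imputation model. Neither document gives an expected share of missing Week 12 values, so I assume 5%, 10% and 20%. I also assume a binary subgroup split 50:50, values missing at random, and a true interaction of 100 mL unless stated.

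**1. The plan's own figure.** SE = 250 × √(1/500 + 1/300) = 18.26 mL. 59/18.26 = 3.23, and 3.23 − 1.96 = 1.27, so power is 89.8%. The stated 90% is reproduced. The plan gives no figure for an interaction.

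**2. Shrinkage with equal missingness.** Let f be the share missing in each arm-by-subgroup cell and δ the true interaction. The completed-data cell mean is (1 − f) × observed mean + f × imputed mean. The imputed means contain no interaction, so the expected estimate is (1 − f) × δ. For δ = 100 mL this is 95, 90 and 80 mL.

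**3. Power.** With complete data the interaction SE is 250 × √(2/250 + 2/150) = 36.5 mL. With 20% missing, observed-data ANCOVA has SE 36.5/√0.80 = 40.8 mL. Then 100/40.8 = 2.45, and 2.45 − 1.96 = 0.49, giving power of about 69%. On imputed data the true spread of the estimate is about 0.80 × 40.8 = 32.7 mL, but Rubin's rules report about 40 mL. Significance then needs 1.96 × 40.3 = 79.0 mL, and an estimate centred on 80 mL reaches that about half the time.

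Simulation (1,500 trials, 500 vs 300, SD 250 mL, 20 imputations, subgroup main effect in the imputation model):

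| Missing | Imputed, mL | Observed data, mL | Rubin SE / actual SD | Power, imputed | Power, observed |
|---|---|---|---|---|---|
| 5% | 95.5 | 100.6 | 37.6 / 34.3 | 74% | 77% |
| 10% | 90.6 | 100.7 | 38.5 / 33.8 | 67% | 75% |
| 20% | 79.8 | 99.9 | 40.3 / 33.4 | 50% | 69% |
| 20%, interaction added to imputation | 100.2 | 100.2 | 41.1 / 41.6 | 67% | 68% |

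Two further simulations at 20% missing gave power of 55% against 72% (residual SD 240 mL) and 52% against 71%. The ratio at 20% stays at 0.80 if the subgroup main effect is left out of the imputation, or if the subgroup is split 20/80.

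**4. Unequal missingness.** Assume 20% missing on placebo (fP) and 10% on active (fA).

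- *Factor absent from the imputation model.* Let g be the subgroup difference on placebo, and suppose the imputed values carry none of it. The expected interaction is (1 − fA)(g + δ) − (1 − fP)g = (1 − fA)δ + (fP − fA)g.

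| δ, mL | g, mL | Formula, mL | Simulated, mL |
|---|---|---|---|
| 0 | 100 | 0 + 10 = 10 | 9.9 |
| 100 | 100 | 90 + 10 = 100 | 101.0 |
| 100 | −100 | 90 − 10 = 80 | 81.7 |
| 50 | 200 | 45 + 20 = 65 | 63.7 |
| 50 | −200 | 45 − 20 = 25 | 25.3 |

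- *Factor present as a main effect.* The multiplier is 1 minus the mean missing share, weighted by 1/(observed cell size). The cells hold 120 observed placebo and 225 observed active patients: (0.20/120 + 0.10/225)/(1/120 + 1/225) = 0.165, so the multiplier is 0.835 (simulated 0.833).

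**5. Key secondary endpoints.** With one earlier visit carrying the same effects in the imputation model and 20% missing, the ratio is 0.90, 0.94 and 0.98 at within-patient correlations of 0.5, 0.7 and 0.9. The loss is about 2% to 10%.

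**6. Split analyses.** If imputation is rerun inside each subgroup at 20% missing, a true 100 mL difference comes out at 101.6 mL (observed data 101.3) and a true 60 mL at 62.6 mL (62.7). There is no shrinkage.

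**The case against.** A reader might infer that every interaction, for every endpoint and in both forms of subgroup analysis, is pulled towards zero by the missing fraction. The documents do not support that. Six factors are outside the imputation model, so unequal missingness can inflate an interaction as well as shrink it (step 4). The key secondary imputation includes other visits (step 5). The SAP does not say whether the split analyses re-impute, and SAP 16.1.4 can be read as imputing within each subgroup (step 6).

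The share imputed may also be small. The 20% in SAP 4.2 is half of a joint condition for adding patients (with withdrawal above 25%), not an expected rate. Off-treatment and end-of-study data are used (SAP 7.3), and 12-hour spirometry counts whenever it was obtained (SAP 6.4), so the imputed share lies below the dropout rate. At 5% missing the power loss is about 3 points. This stands. Some gaps are nevertheless foreseeable: follow-up by phone only or with a clinic return only at Week 24 (Protocol 7.2.2, 7.2.3), optional spirometry after stopping study drug (7.3.1.1), required withdrawal for active COVID-19 (7.1.6), and no AUC without a pre-dose value (SAP 16.1.1.1).

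The bias is modest beside the noise. For a true 60 mL interaction at 20% missing it is 60 − 48 = 12 mL, about 0.3 of a Rubin SE of 38.7 mL. Root mean squared error was in fact lower with the planned imputation than with observed-data ANCOVA: 32.9 against 39.1 mL for a 60 mL interaction, and 35.7 against 37.7 mL for 100 mL. The 60 mL test is weak either way (power 34% observed, 23% imputed). All this supports a minor rating. But the lower error comes from pulling the estimate towards no difference, which is no merit in a test for a difference.

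Finally, the observed-data analyses in SAP 16.1.4 do not already answer the point. What that bullet calls subgroups are two rules for which data to include, and neither is crossed with the factors of SAP 7.5.

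**Conclusion.** Wrong as written, minor severity. The defect is certain for one analysis: the pooled interaction test of the primary endpoint. With similar missingness by arm, the estimate shrinks by about the share of Week 12 values actually imputed, and the inflated standard error lowers power further: about 3 points at 5% missing, 8 at 10% and 17 to 19 at 20%, for a 100 mL interaction. With different missingness by arm, an omitted factor that predicts outcome can push the interaction either way. In the example with no true interaction, the spurious 10 mL did not raise the false-positive rate (2.3%, against 4.9% with observed data), because the standard error was too large.

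These sizes rest on assumed missing shares, interaction sizes and subgroup main effects, none of which the documents give. The leakage figures also assume that baseline FEV1 does not stand in for the omitted factor, which may be less true for COPD severity. Subgroup tests lie outside the hierarchy in SAP 7.4, so the primary and key secondary conclusions do not change.

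**What to change.** In SAP 7.5, 16.1.4 and 16.2.4, state that:

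- for each pooled subgroup analysis, the imputation model includes the subgroup and its interaction with treatment;
- alternatively, for the primary endpoint, the interaction is tested by ANCOVA on all observed data, on or off treatment. SAP 16.1.2 requires a non-missing baseline and uses no other post-baseline visit, so this loses almost no information. It is the better choice for small cells such as Asia;
- split analyses rerun the imputation within each subgroup.

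The cost is a few lines of SAP text and code, and one imputation run per subgroup factor. Imputing separately within every arm-by-subgroup cell would also remove the bias but is less robust. ICS users are limited to 20% of patients (Protocol 4.1), about 0.20 × 300 = 60 on placebo if balanced, and the weekly E-RS imputation uses more than 20 weekly means as predictors.

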16.2. SECONDARY EFFICACY

The secondary efficacy analyses will be performed for the mITT population. These include:

- Change from baseline FEV₁ to peak FEV₁ on Day 1 and at Weeks 6, 12 and 24
- Change from baseline (i.e. mean over the last 7 days of run-in) to the mean weekly value at Weeks 6, 12 and 24 in COPD symptoms, as measured by daily diary (E-RSTM:COPD)
- Change from baseline in the SGRQ total score at Weeks 6, 12 and 24
- Change from baseline FEV₁ to morning trough FEV₁ at Weeks 6, 12 and 24
- Change from baseline FEV₁ to average FEV₁ AUC_{0-4h} on Day 1 and at Weeks 6, 12 and 24
- Proportion of SGRQ responders at Weeks 6, 12 and 24
- Change from baseline (i.e. mean over the last 7 days of run-in) to the mean weekly value in the number of puffs of rescue medication at Weeks 6, 12 and 24
- TDI questionnaire at Weeks 6, 12 and 24
- Change from baseline FEV₁ to evening trough FEV₁ at Week 12

16.2.1. SECONDARY EFFICACY VARIABLES & DERIVATIONS

16.2.1.1. Spirometry

Spirometry measurement's best test time which is used in the analysis is measured in ERT and first time for spirometry measurements is measured in the eCRF and will be listed alongside the ERT best time.

Peak FEV₁ will be computed as the maximum value in the 4 hours after dosing (4 timepoints after dosing: 30 minutes, 1 hour, 2 hours and 4 hours). Baseline FEV₁ is the average of the two measurements taken before study medication on the day of first dosing, i.e. ≤40 minutes pre-dose on Day 1.

Average FEV₁ AUC_{0-4h} is calculated as described in Section 16.1.1.1 of the SAP.

Morning trough FEV₁ is the last value collected prior to the morning dose.

Evening trough FEV₁ is the value collected at the 12 hours post-morning dose timepoint and prior to the evening dose.

All measurements, including unscheduled measurements, within specified time period will be used for deriving parameters; for scheduled 12 hours post-morning dose measurement use regardless of being within specified time period.

16.2.1.2. Questionnaires

16.2.1.2.1. E-RS™:COPD

EXACT-Respiratory Symptoms for COPD (E-RS™: COPD) data will be collected within EXACT-PRO questionnaire (consisting of 14 questions), as shown in Appendix 3. Please note that items 3, 8, 9, 10, 11 and 14 have separate scoring instructions, namely with the same raw score being assigned to several answer options. E-RS™: COPD consists of 11 questions, with subdomains of: Breathlessness, Cough and Sputum, and Chest Symptoms. This data will be collected everyday throughout the duration of the study.

Calculating the score

E-RS subdomains:

- Breathlessness – items 7, 8, 9, 10 and 11 (score range: 0-17)
- Cough and Sputum – items 2, 3 and 4 (score range: 0-11)
- Chest Symptoms – items 1, 5 and 6 (score range: 0-12)

The E-RS Total score is derived as the sum of the raw scores of the 11 items (score range: 0-40). Total and subdomain scores are derived weekly as the mean over the days within each window, as specified in the Section 6.4 of the SAP, using only days where data was recorded. Baseline is the mean over the 7 days prior to the first intake of study treatment, using only days where data was recorded. If less than 4 days of data are available for the week, the weekly mean is set to missing. Furthermore, all questions need to be answered to be evaluable for that day.

If a patient discontinued then use treatment study end date, as the date of their last expected visit.

The EXACT-PRO total score will be calculated by first summing the raw scores of all 14 items (score range: 0-51) and then looking up the corresponding EXACT-PRO total score in the table described in the Appendix 4 (converted score range: 0-100).

E-RS subdomain score is calculated as the sum from the relevant questions.

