- Laboratory tests

Overall Design

RPL554-CO-301 is a multicenter, randomized, double blind, parallel group, placebo controlled study to determine the efficacy and safety of ensifentrine 3 mg twice daily (BID) for 24 weeks with a subset of patients for 48 weeks, administered via nebulizer vs. placebo in patients 40 to 80 years of age with moderate to severe COPD (FEV₁ 30% – 70% of predicted, FEV₁/forced vital capacity (FVC) ratio <0.7, with documented COPD symptoms).

Approximately 50% of patients recruited will be using stable background maintenance as *either* long-acting muscarinic antagonist (LAMA) *or* long-acting β 2 agonist (LABA) maintenance therapy and all patients will be provided with rescue albuterol/salbutamol for use as needed during the study. Up to 20% of patients are allowed to take inhaled corticosteroids during the study under certain provisions (see Sections 6.7.2 and 6.7.3). Washout of patients on stable background maintenance LAMA or LABA monotherapy for the sole purpose of study eligibility is not recommended.

Randomization in RPL554-CO-301 will be stratified by three different factors: treatment duration (48 or 24 weeks), stable background maintenance LAMA or LABA therapy use (yes or no), and cigarette smoking (current or former). The 48 weeks strata will be randomized active to placebo 3:1, and the 24 weeks strata will be randomized active to placebo 1:1. Patients in the stable background maintenance LAMA or LABA therapy stratum must withhold Twice-Daily LAMA or LABA (or LAMA/ICS or LABA/ICS) for 24 hours and Once-Daily LAMA or LABA (or LAMA/ICS or LABA/ICS) for 48 hours prior to initiation of any spirometry. All patients must withhold short acting bronchodilator (SABA) rescue medication for at least 4 hours prior to initiation of any spirometry. The 48-week subset is intended to inform on the long-term safety of ensifentrine vs placebo and the 3:1 randomization in this subset is intended to minimize the number of patients randomized to placebo for 48 weeks.

All sites will use standardized spirometry and electrocardiogram (ECG) equipment provided by a central vendor and all spirometry and ECGs will be over-read by the blinded central vendor.

Patients will be screened for eligibility before entering a 28-day run-in period to ensure a stable COPD treatment regimen and to collect baseline information on symptoms and rescue medication use. Permitted rescue and background medications and the condition of

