	Screening 1 day Clinic Visit ¹	Run- in 28 Days ± 4 Days	Day 1 (Rand) Clinic Visit ¹	Week 6 Clinic Visit ^{1,2}	Week 12 Clinic Visit ^{1,2}	Week 18 Phone Contact	Week 24 Clinic Visit ^{1,2}	Week 30 Phone Contact	Week 36 Flexible Visit ²	Week 42 Phone Contact	Week 48 Clinic Visit	Follow up Phone Contact ³	Early Term/ Withdrawal ⁴	Procedures for Early Term/Withdrawal (24 or 48-Week Subset) Follow up Phone Contact ³
	V0	V1	V2	V3	V4	V5	V6	V7	V8	V9	4 to 10 Days after Week 24 or Week 48	ET/ Withdrawal	4 to 10 Days After Early Term	
Health Outcomes ¹¹														
SGRQ		X	X	X										
EQ-5D-5L		X		X										
BDJ		X												
TDI			X	X	X									
Healthcare Utilization Assessment	X	X	X	X	X	X	X	X	X	X	X	X	X	X
Patient Perception Survey														X
Issue eDiary to Patients Eligible to Enter Run-in	X													
Assess eDiary and E- RS/EXACT-PRO Compliance (E-RS will be on eDiary) ¹²			X	X	X	X	X						X	
Collect eDiary													X	
Safety Assessments														
Vital Signs ¹³	X		X	X	X	X	X	X	X	X	X	X	X	X

Table 3: Schedule of Activities

Study Assessments and Procedures	Procedures for Patients Completing Either the 24-Week or the 48 Week ¹⁹ Subset													Procedures for Early Term/Withdrawal	
	Screening 1 day Clinic Visit ¹	Run-in 28 Days ± 4 Days	Day 1 (Random) Clinic Visit ¹	Week 6 Clinic Visit ^{1,2}	Week 12 Clinic Visit ^{1,2}	Week 18 Phone Contact	Week 24 Clinic Visit ^{1,2}	Week 30 Phone Contact	Week 36 Flexible Visit ²	Week 42 Phone Contact	Week 48 Clinic Visit	Follow up Phone Contact ³	Early Term/Withdrawal ⁴	Follow up Phone Contact ³	Procedures for Early Term/Withdrawal
	±10 Days	±10 Days	±10 Days	±10 Days	±10 Days	±10 Days	±10 Days	±10 Days	±10 Days	±10 Days	±10 Days	4 to 10 Days after Week 24 or Week 48	ET/Withdrawal	4 to 10 Days After Early Term	
V0			X	X	X	X	X	X	X	X	X	X			
12-Lead ECG (pre-dose) ¹⁴	X		X	X	X		X	X	X	X	X		X		
12-Lead ECG (1.5 hours post dose) ¹⁴			X	X	X		X	X	X	X	X		X		
Physical Examination	X														
AE Assessment			X	X	X	X	X	X	X	X	X	X	X	X	X
Laboratory Assessments															
Laboratory Tests															
Haematology, Chemistry (non-fasting), Pregnancy Test (serum) ¹⁵	X		X				X				X		X		
Urine Pregnancy Test for Women ¹⁵			X	X					X						
Viral Serology for hepatitis	X														
Optional COVID-19 Test ¹⁶	Optional		Optional	Optional	Optional		Optional		Optional		Optional		Optional		Optional
Blinded Study Medication, Rescue Medication, Nebulizers and Compressor ¹⁷															

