5.3 Randomization Criteria

Criteria for Inclusion at Randomization

1. Symptoms of COPD: A score of ≥ 2 on the mMRC Dyspnea Scale at Visit 1.
2. Completion of the e-Diary at least 5 of the last 7 days of the Run-in period.

Criteria for Exclusion from Randomization

1. COPD exacerbation or lower respiratory tract infection between Screening and Randomization (defined as use of any additional treatment other than current treatment and rescue medication and/or emergency department or hospital visit). Patients with a severe COPD exacerbation that requires hospitalization may not be rescreened.
2. Positive COVID-19 result at Screening or between Screening and Randomization.
3. Prohibited medication use between Screening Visit 0 and Visit 1.
4. Significantly abnormal ECG finding as defined in Section 11.4 on the 12-lead ECG obtained at Screening as assessed by the investigator or site medical doctor/medically qualified person or on the pre-dose ECG obtained at Visit 1 *before the patient has been randomized*. After a patient has been randomized, ECG withdrawal criteria (Section 11.5) will apply. In the event that the central ECG reviewer discovers a significant ECG abnormality meeting ECG withdrawal criteria on the Visit 1 ECG in 2 of 3 triplicate measurements, the patient may be discontinued.
5. Did not meet one or more of the Inclusion Criteria (Section 5.1) or met one or more of the Exclusion Criteria (Section 5.2) as assessed at Screening Visit 0 (e.g. including overreads or lab values obtained after the day of Screening).

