8.1.13 Electronic Diary Activities

Electronic Diary training will be conducted as described in Section 8.5.4 and the eDiary will be issued for use during the study. Patients will be instructed to enter their daily symptoms (E-RS:COPD/EXACT-PRO questionnaire), rescue medication (puffs per day), and maintenance LAMA or LABA medication (if applicable) into the eDiary each day.

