16.2.1.3. Rescue Medications

Baseline use of rescue medication is the mean over the last 7 days of run-in phase, using only days where data was recorded:

$$\frac{\text{Sum of number of puffs taken}}{\text{days recorded}}$$

Use of medication per week is calculated as the mean use daily over 7 days, as described in the windowing conventions Section of the SAP, calculated only based on the days data was recorded/verified.

If less than 4 days of data are available for the week, the weekly mean is set to missing. If a patient discontinued then use study discontinuation end date, as the date of their last expected data input.

This will be documented as Albuterol/Salbutamol in the “Rescue Medication” page of the eCRF, as well as in the “Rescue Medication Use” diary entry.

The rescue medication use will be confirmed in the diary using the following rules:

1. If patient has put in rescue medication use then analyze as expected.
2. If patient has not put in rescue medication use, then to confirm that there was no diary compliance issue, or IT issue, question “No Rescue Medication Confirmation” will be checked to make sure it is filled in correctly.
3. If patient has not put in rescue medication use and question “No Rescue Medication Confirmation” was not filled in correctly then this will be treated as diary compliance or IT issue and therefore this day will not be used as the day recorded for the weekly means calculation.

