16.2.3. ANALYSIS OF SECONDARY EFFICACY VARIABLES

16.2.3.1. Change from baseline variables, incl. TDI

All variables used in change from baseline analysis (incl. average FEV₁ AUC_{0-4h}, peak FEV₁, morning trough FEV₁, evening trough FEV₁, mean weekly E-RSTM:COPD, SGRQ, mean weekly rescue medication and TDI) will be analyzed using ANCOVA approach, as described in Section 16.1.3 of the SAP. BDI will be used as a baseline for TDI. Missing data will be imputed using imputation described in Section 16.2.2 of the SAP. Continuous method will be used for lung function endpoints and the main analysis. Range method will be used for corresponding sensitivity analyses of SGRQ total score and weekly mean E-RS total score and the main analysis of TDI.

Model assumptions will be tested and solved, if failed, as per Section 16.1.3 of the SAP.

A plot of the mean change from baseline FEV₁ to each post-dose FEV₁ result over time will be created by subgroups of actual background medication strata and actual smoking strata, visit and treatment group.

A plot of the least squares means change from baseline to event over time will be presented (based on the ANCOVA analysis). Events will include weekly mean total E-RS score, SGRQ and weekly mean rescue medication use.

Only FEV₁ measurements with BTR grades “Acceptable” and “Borderline Acceptable” are used in the analysis.

[REDACTED]

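### The E-RS and rescue-use models adjust only for the last 7 of about 28 diary run-in days; adding the earlier run-in mean would probably give a modest gain in precision

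*SAP*

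**What the plan says.** The Protocol synopsis sets out the run-in: "Patients will be screened for eligibility before entering a 28-day run-in period". One of its two stated purposes is "to collect baseline information on symptoms and rescue medication use"; the other is to secure a stable COPD treatment regimen. The Schedule of Activities allows 28 days plus or minus 4 and lists, at Screening, "Issue eDiary to Patients Eligible to Enter Run-in". Protocol 8.1.13 has patients enter E-RS symptoms and rescue puffs each day from then on.

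The SAP uses only the last week of these entries. For E-RS (SAP 16.2.1.2.1): "Baseline is the mean over the 7 days prior to the first intake of study treatment, using only days where data was recorded". For rescue use (SAP 16.2.1.3): "Baseline use of rescue medication is the mean over the last 7 days of run-in phase".

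Under SAP 16.2.3.1 both endpoints "will be analyzed using ANCOVA approach, as described in Section 16.1.3 of the SAP". That model has treatment, region, background-medication stratum, smoking stratum and a single baseline covariate. For weekly endpoints, the imputation model in SAP 16.2.2.1 uses that baseline and the post-dose weekly means. The week windows in SAP 6.4 start at Day 1, so no run-in week is defined for it to use.

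E-RS at Week 24 is third of the seven ordered tests in SAP 7.4. Rescue use is a secondary endpoint outside that order.

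**The concern.** A one-week mean contains week-to-week fluctuation as well as the patient's usual level. When the usual level is what predicts Week 24, averaging over more pre-treatment days gives a better predictor and leaves less unexplained variance in the treatment comparison. Here the extra days are already collected and about three-quarters of them (21 of 28) are left out of the models.

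What is at stake is precision, not bias. For E-RS, precision matters beyond the endpoint itself: if the third test fails, SGRQ total, morning trough FEV1, FEV1 AUC0-4h and the SGRQ responder proportion cannot be claimed. That argument does not extend to rescue use.

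**Working it through.** **The plan's own figure.** Protocol 9.2 gives 90% power for 59 mL in FEV1 AUC0-12h, with SD 250 mL, 500 versus 300 patients and a two-sided 5% test. This reproduces: 89.8% power, or about 805 patients for 90%. It is the only power figure in the documents and says nothing about E-RS or rescue use. The sizes below therefore rest on assumed correlations and an assumed 80% starting power.

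**Formula.** Let r1 be the correlation of the last-week mean with Week 24, r2 that of the earlier run-in mean with Week 24, and r12 that between the two run-in means.

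- R² with both covariates = (r1² + r2² − 2·r1·r2·r12) / (1 − r12²)
- Residual-variance ratio f = (1 − R²) / (1 − r1²)
- Power after the change = Φ((1.96 + 0.842)/√f − 1.96), starting from 80%

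**Worked case.** Take r1 = r2 = 0.6 and r12 = 0.9. R² = (0.72 − 0.648)/0.19 = 0.379. f = 0.621/0.64 = 0.970. Power = Φ(2.802/0.985 − 1.96) = 81.2%.

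**No-gain case.** If r2 = r1·r12, the earlier days add nothing beyond the last week. The formula then gives R² = r1², so f = 1.00 and power stays at 80%.

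**Range.**

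| Assumption | f | 80% becomes |
|---|---|---|
| Earlier days add nothing (r2 = r1·r12) | 1.00 | 80% |
| r1 = r2 = 0.5, r12 = 0.95 | 0.991 | 80.3% |
| r1 = r2 = 0.6, r12 = 0.90 | 0.970 | 81.2% |
| r1 = r2 = 0.7, r12 = 0.80 | 0.893 | 84.2% |
| Stable level + decaying state + daily noise + long-term change to Week 24 (r1 0.57 to 0.77, r12 0.88 to 0.96) | 0.981 to 0.913 | 80.8% to 83.5% |
| Decaying state only, no stable level (half-life 300 days) | 0.999 | 80.0% to 80.1% |

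A fall of 10% (f = 0.90) gives Φ(2.802/0.949 − 1.96) = 84%, which sets the upper end of the summary range. From a higher start the gain is smaller: a 5% fall adds about 2.0 points at 80% power, 1.4 at 90% and 0.9 at 95%.

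**Cost of a useless covariate.** One degree of freedom out of about 790 gives 792/791 = 1.0013, a variance increase of about 0.13%.

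**Missing early diaries.** The randomisation criterion is "Completion of the e-Diary at least 5 of the last 7 days of the Run-in period"; nothing is required of the earlier days. In the scenario with f = 0.91, 2,000 simulated trials with mean fill plus a missing indicator gave variance ratios of 0.89 (no missing; the gap from 0.91 is simulation error), 0.95 (10% missing) and 0.98 (30% missing). Setting the second covariate equal to the 7-day mean keeps more. In models where the full-data fall was 6 to 11%, variance still fell 5 to 10% with 10% missing and 4 to 7.5% with 30% missing.

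**The case against.** The strongest reply is that this is an efficiency preference and that the last week is a defensible baseline. Early run-in may be a settling period. The run-in also exists to stabilise treatment, and Protocol Table 8 lets some medicines stop only 48 hours (theophylline, PDE4 and leukotriene inhibitors) or 6 hours (ipratropium) before Screening. For those patients the early days may predict Week 24 less well. This stands. It is a reason to keep the 7-day baseline for the change score and to expect a modest gain. It is not a reason to leave the earlier mean out of the covariates, because the model estimates its weight and a useless term costs almost nothing.

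The weekly imputation model already conditions on post-baseline weekly means, which lie closer to Week 24 than early run-in. So the gain within the imputation step itself is unproven. The covariate belongs there mainly so that the imputation and analysis models agree.

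The E-RS analysis also feeds the per-protocol, average-imputation, tipping-point, range-imputation, subgroup and Extended mITT analyses, and CO-302 is described as otherwise identical over 24 weeks. That cost is real but small.

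Three stronger readings are tempting, and the documents do not support them:

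- *The baseline may rest on only 4 days.* Four is the SAP's general floor for a weekly mean. The 5-of-7 randomisation criterion normally secures at least 5.
- *The gain is large.* Falls of 17% (r1 = 0.7, run-in weeks correlated 0.8) or 20 to 35% (all weeks equally correlated) require each early run-in week to predict Week 24 as well as the final week does. Nothing in the documents establishes that.
- *E-RS is underpowered.* No E-RS power is given. Protocol 2.2 reports a significant E-RS effect in a 403-patient Phase IIb study over 4 weeks, so power above 80% is at least as plausible, although persistence to Week 24 is unknown.

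**Conclusion.** The point holds as an optional improvement. The planned E-RS and rescue-use analyses are valid and unbiased; they use less of the collected baseline data than they could. Adding the earlier run-in mean is likely to reduce residual variance by roughly 0 to 10%. At an assumed 80% power that is about 0 to 4 points, or at most the information of about 89 more patients (800/0.90 = 889).

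The estimate depends on within-patient correlations that neither document reports. It shrinks when early diaries are incomplete and vanishes if the last week already carries all the predictive information. Confidence in the direction is good; confidence in the size is low. The link to the later ordered tests applies to E-RS only.

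**What to change.** Before unblinding, amend SAP 16.2.2.1 and 16.2.3.1 for weekly mean E-RS total and weekly rescue use:

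- Keep the 7-day baseline for the change score and as a covariate.
- Add the mean of the recorded run-in days from -28 to -8 as a second baseline covariate, in both the linear ANCOVA and the imputation models.
- If fewer than 4 of those earlier days are recorded, set the second covariate equal to the 7-day mean, so that no patient is lost.
- Leave the responder logistic models unchanged. An odds ratio depends on which prognostic covariates are conditioned on, so adding one there would change the quantity being estimated.

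The correlation between the two run-in means, and the completeness of the early diary, can be checked on blinded data alongside the model checks already planned in SAP 16.1.3.

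The cost is one derived variable and SAP wording, carried through the related sensitivity analyses and aligned with the CO-302 and pooled SAPs. No new data are needed. For these linear models the endpoint, estimand and baseline definition do not change.
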